NMES will be carried out bilaterally on the quadriceps using a portable stimulation device (EMPI Continuum or 300PV). Study personnel will teach volunteers to use the NMES device and provide detailed directions for its use (Appendix IX). Briefly, two adhesive electrodes will be affixed to anterior surface of each thigh: ~1 cm distal to the inguinal crease and ~5 cm proximal to the patella, with the leg maintained in isometric conditions by placing a bolster under the knees and using ankle weights. Symmetrical, biphasic pulses (400 µs duration at 50 Hz) will be used, with a duty cycle of 25% (10 s on, 30 s off) at stimulation intensities sufficient to cause visible muscle contractions below pain threshold. NMES sessions will occur 5 d/wk for 1 hr/d (two 30 min or one 60 min session) for 8 wks. This regimen (lower duty cycle and 60 min/d) differs slightly from that put forth in the grant proposal in lieu of reviewer's comments on the resubmission and consultation with our co-investigator ([name]), as well as comments from volunteers in our VCC/LCCRO Pilot Project Grant, where volunteers suggested that we offer shorter sessions, as finding time for longer sessions was problematic for women with family and work commitments. We will monitor adherence to the NMES program covertly using the compliance monitoring feature built in to the NMES device software. Additionally, volunteers will self-report compliance, stimulation intensity and muscle soreness/side effects (Appendix VIII and X) and these reports will be reviewed during weekly phone contacts by study personnel. Finally, we will assess acceptability of the program using a questionnaire. These measures are taken to inform future RCTs if our hypotheses are supported.

Attention control patients will not receive an NMES device. They will receive weekly phone calls to discuss measurements of leg muscle soreness to standardize the amount of interaction with study personnel to the NMES group.

1. [name], M. J., Miller, M. S., Callahan, D. M., Sweeny, A. P., Nunez, I., Grunberg, S. M., Der-Torossian, H., Couch, M. E., and [name], K. (2013) Molecular mechanisms underlying skeletal muscle weakness in human cancer: reduced myosin-actin cross-bridge formation and kinetics. *J Appl Physiol* **114**, 858-868

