Patients will be encouraged to adjust stimulation to a tolerable level and will have full control over the stimulator to continue to make adjustments as necessary. During the first couple of NMES sessions, muscle soreness may occur. The level of fatigue and/or soreness will be similar to that which occurs following a standard exercise training session and will dissipate over time as the volunteer's muscles become accustomed to the electrically-stimulated contractions (ie, they become trained). Nonetheless,

in response to concerns of the NIH reviewers, we have instituted a regimen of assessing muscle pain each week using a hand-held pressure algometer, with results being reviewed with volunteers during weekly phone contacts. Volunteers will be instructed on how to assess muscle soreness manually at standardized points along their quadriceps. Briefly, the volunteer will provide 2 kg/cm² of pressure using the algometer at each site, which will provide mild pressure over 1 cm²-size of rubber algometer probe that will be below pain threshold. If muscle soreness related to the NMES is present, there may be mild soreness/pain at the site of algometer testing and the volunteer will note her level of discomfort using the Wong pain scale (0-10). Any level of discomfort greater than 6, or if the patient reports muscle soreness that hinders simple activities of daily living, such as walking, the research coordinator will contact the PI for referral to the Safety Officer. The Safety Officer will then follow up with the patient by phone (or in person, if deemed necessary) to assess the volunteer's level of discomfort and whether she should continue in the study. In our past experience with exercise training and NMES, there is some level of discomfort expected as the muscle is trained. However, in all cases, muscle soreness has not been sufficient that volunteers have chosen to discontinue the study or that it substantially hinders daily activities.

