Therapeutic Alternatives:

NMES seeks to provide an exercise training stimulus to volunteers to help maintain skeletal muscle size and functionality. During treatment, there is generally not an alternative exercise program available, as our institutional oncology rehabilitation program does not typically begin until after treatment is complete. This lack of therapeutic alternatives during treatment was a primary impetus for undertaking these studies. Volunteers can chose to exercise on their own, however, and not participate in the current study.

Data Safety and Monitoring:

Our study is a clinical trial, but not a phase III clinical trial. Thus, pursuant to NIH regulation, we will establish a formal Data Safety Monitoring Plan, which will provide additional oversights to further protect against risk to safety and confidentiality.

The PI ([name]) and [name] will monitor the safety of the research procedures for this study. [name] will be available on-site for all major experimental procedures (eg, muscle biopsy) that might reasonably be expected to pose safety concerns for volunteers. In this context, the PI will be readily available to monitor volunteer safety throughout the study. If an event occurs that affects participant safety, the PI and/or [name] will alert the Safety Officer ([name]), who will adjudicate the event with respect to its severity, expectedness and relatedness to participation in the study according to the aforementioned criteria. Because numerous clinical trials in our laboratory have demonstrated the safety of this regimen of testing in patients from a broad range of clinical backgrounds (eg, heart failure patients, cancer survivors, healthy elderly), we expect minimal problems related to testing. NMES is generally a very safe intervention, having been used in a variety of acute and chronic conditions, from heart failure patients awaiting transplant to ICU patients. Additionally, we will actively monitor volunteers at regular intervals (weekly phone calls) to assure that no problems develop. Thus, we do not feel that it is reasonable to incorporate "stoppage criteria" for the overall study. Instead, the Safety Officer will decide whether an individual participant should continue with the study following occurrence of any adverse events or unanticipated problems taking into consideration what is in the best interest of that individual, including instances of undue muscle soreness related to the NMES device.

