Adverse Event and Unanticipated Problem (UAP) Reporting:

Adverse events will be reported by one of 3 mechanisms. First, the UVM/UVM Medical Center Committee for Human Subject Research Adverse Event Reporting Form. Report of any event will be forwarded to the office of the Committee for Human Research in the Medical Science (CHRMS) within 2 days of the PI learning about the event. Reporting adverse events will be the responsibility of the PI. The CHRMS will determine whether additional reporting requirements are indicated. Second, the Patient Safety Reporting system (SAFE) through UVM Medical Center can also be used, which may be initiated by clinical research center staff or study personnel. These forms will be forwarded within 3 days to the PI, UVM Medical Center Risk Management Office, CHRMS and other appropriate agencies, as indicated by the nature of the report. Finally, the UVM Medical Center Medication/IV Event Report Form, with distribution and timing as noted above. This latter mechanism might be used with events related to blood sampling or other invasive procedure, such as the biopsy. Reviews of protocol specific adverse events will be performed no less than annually. Additionally, any adverse event that occurs will be forwarded to the PI for reporting to the Human Subject Research Protection Office within 1 week of occurrence. Of note, these protections against risk include both physical risks to the volunteers, as well as risks associated with any breach in confidentiality.

On an annual basis, Drs. [name] and [name] will assess data being gathered and safety of volunteers to assess the pattern or frequency of events to identify occurrence of any event or problem that significantly alters the safety profile of the procedures being performed, unless occurrence of a serious adverse event or unanticipated problem necessitates re-evaluation of the expected risk of the study procedures at an earlier time point. Additionally, [name] will evaluate data collection and storage to ensure the confidentiality of data and quality. Each of these evaluations will be followed by reports of study progress and patient safety to the University of Vermont Committee on Human Research in the Medical Sciences via yearly progress reports and to the appropriate NCI program officer. The report will include information regarding study status, participant information and safety information. This report will also be forwarded to the Safety Officer for his review.

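### As written, weekly contacts review side effects in the NMES arm but only leg soreness in controls, so event counts by arm will not be comparable unless the call content is aligned

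*Combined protocol and SAP*

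**What the plan says.** The Treatment Phase section (under Procedures) describes the weekly contact separately for each arm.

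- NMES arm: "volunteers will self-report compliance, stimulation intensity and muscle soreness/side effects (Appendix VIII and X) and these reports will be reviewed during weekly phone contacts". With the acceptability questionnaire and the device's own compliance record, the stated purpose is: "These measures are taken to inform future RCTs if our hypotheses are supported".
- Attention control arm: "They will receive weekly phone calls to discuss measurements of leg muscle soreness to standardize the amount of interaction". The aim given is to match the amount of contact. No question about side effects or other events is mentioned.

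Three other places bear on the point.

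- Risks/Benefits, within the NMES risk text, describes the soreness measurement: "we have instituted a regimen of assessing muscle pain each week using a hand-held pressure algometer".
- Data Safety and Monitoring says, without naming an arm: "we will actively monitor volunteers at regular intervals (weekly phone calls) to assure that no problems develop". It also makes the Safety Officer the person "who will adjudicate the event with respect to its severity, expectedness and relatedness to participation in the study".
- Adverse Event and Unanticipated Problem (UAP) Reporting sets an annual review to "assess the pattern or frequency of events to identify occurrence of any event or problem that significantly alters the safety profile".

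Adverse events are not among the primary or secondary outcomes listed under Procedures, and the Statistical Analysis Plan contains no comparison of them between arms.

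**The concern.** An attention control that matches contact time does not necessarily match how events are found. On the Treatment Phase wording, a woman on NMES is prompted every week about side effects. A control with the same symptom is prompted about leg soreness and must volunteer anything else.

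This matters because much of what could be reported is not specific to the device. Every participant is receiving chemotherapy, both arms have biopsies, and either arm may include women who pause prophylactic anticoagulation around the biopsy. The controls are the only concurrent source of a background rate for such events. If that rate is collected with less prompting, ordinary treatment effects can appear as an excess on NMES, and milder events in controls can go unrecorded.

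The calls are also a stated safeguard: Data Safety and Monitoring lists them among the reasons for having no study-level stopping criteria. What is asked in them should therefore be explicit and the same for all participants.

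**Working it through.** **Step 1: the passages side by side.**

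| Place | Arm | Content stated |
|---|---|---|
| Treatment Phase, NMES paragraph | NMES | compliance, intensity, soreness, side effects; reviewed by phone |
| Treatment Phase, attention control paragraph | Control | leg muscle soreness |
| Risks/Benefits, NMES text | Not stated to include controls | weekly algometer soreness |
| Data Safety and Monitoring | All volunteers | weekly calls to check for problems; no questions listed |

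Soreness is discussed in both arms. Side effects are named for NMES only. The general monitoring statement neither contradicts nor confirms this, because it lists no questions.

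**Step 2: is there another scheduled source of events common to both arms?** None is described.

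- The reporting routes in the UAP section start once someone knows of an event.
- The questionnaires under Procedures cover fatigue, activity, general health and neuropathy. They belong to baseline and post-intervention testing.
- Sources of Materials allows data from medical records but sets no scheduled review for events.

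**Step 3: how large could the distortion be?** The plan gives no adverse event rate, capture rate or safety comparison, so there is no figure to reproduce. The following is an illustration, and every risk and capture probability in it is an assumption. Only the 12 per arm comes from the Study Design section.

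Let p be the true risk of a non-soreness event, equal in both arms. Let c_N and c_C be the probabilities that such an event is recorded on NMES and in controls.

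- Observed rate = p × c.
- Apparent risk ratio = (p × c_N)/(p × c_C) = c_N/c_C, which does not depend on p.
- Apparent absolute gap = p × (c_N − c_C).

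With c_N = 0.9:

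- c_C = 0.7: 0.9/0.7 = 1.29
- c_C = 0.5: 0.9/0.5 = 1.80
- c_C = 0.3: 0.9/0.3 = 3.00

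For p from 0.2 to 0.6, the absolute gap runs from 0.2 × (0.9 − 0.7) = 0.04 to 0.6 × (0.9 − 0.3) = 0.36.

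At 12 per arm with c_N = 0.9 and c_C = 0.5 (exact binomial calculation):

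| True risk p | Observed rates | Expected women with an event | Chance NMES shows more | Same, capture 0.9 in both arms |
|---|---|---|---|---|
| 0.2 | 0.18 vs 0.10 | 2.2 vs 1.2 | 0.61 | 0.39 |
| 0.4 | 0.36 vs 0.20 | 4.3 vs 2.4 | 0.75 | 0.42 |
| 0.6 | 0.54 vs 0.30 | 6.5 vs 3.6 | 0.85 | 0.42 |

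Over all the unequal-capture settings (c_C from 0.7 to 0.3, p from 0.2 to 0.6), Fisher's exact test would give p<0.05 in about 1% to 31% of such trials. The distortion would therefore show mostly in the raw counts and would seldom be flagged by a test.

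**Step 4: with the same asking in both arms.** If c_N = c_C, the apparent risk ratio is 1.00 at any true risk.

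**The case against.** The case against has five parts.

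1. Data Safety and Monitoring refers to the same weekly calls and does not limit them to one arm. The control sentence in the Treatment Phase section may only explain why controls are called, and need not list everything asked. This stands in part. It makes unequal asking an inference from the wording rather than a certainty. It does not remove the difference, because the general statement names no question or form.

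2. The NMES self-report may be a device log, since side effects appear beside compliance and stimulation intensity. The forms are in Appendices VIII and X, which are not in the text available here. Appendix VIII is also cited for the questionnaires in the general testing procedures. This stands as a limit on certainty: the forms may already be common to both arms.

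3. No between-arm adverse event analysis is planned, and the annual review is oversight rather than a comparison of arms. This stands. The point is about whether counts by arm could be read, not about an error in a specified analysis.

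4. Serious events have routes that do not depend on the call, including the hospital safety reporting system and medical records. Hospitalization beyond 48 hours is also a removal criterion. This stands for serious events. Milder events have no such backstop described.

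5. The illustrated ratios are simply ratios of assumed capture probabilities. This is correct, and they are offered only to show a range.

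**Conclusion.** The point holds as a correctable gap in data collection. The Treatment Phase section states different content for the weekly contact in the two arms, and Data Safety and Monitoring does not resolve the difference. If the Treatment Phase wording is followed, counts of non-soreness events by arm will not be comparable, most likely with more recorded on NMES, and milder control-arm events may be missed. With no true difference, the apparent risk ratio would be about 1.3 to 3.0 if capture is 0.9 on NMES and 0.7 to 0.3 in controls. Those capture rates are assumptions, not properties of this trial.

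Three stronger readings are tempting but not supported.

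- A reader might infer that a planned safety comparison is biased. No such comparison is planned, and the primary fibre and mitochondrial analyses are unaffected.
- A reader might infer that the Safety Officer's relatedness judgements are biased. Each event is judged against participation in the study. Unequal asking changes which events reach that step, and no effect on the judgement itself is shown.
- A reader might infer that clots or other serious events in controls would go undetected. The other reporting routes make that too strong.

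**What to change.** Reconcile the Treatment Phase section with Data Safety and Monitoring by stating that one arm-neutral weekly adverse event question and form is used in both arms. It should cover soreness, any new symptom or medical event, hospital contact and new medicines. Keep compliance, stimulation intensity and electrode-site items as a separate NMES-only add-on, reported for that arm alone. State that any table of events by arm uses the common form only.

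The control calls are already scheduled, so the cost is a revised form and slightly longer control calls. If the forms and call script in use are already the same in both arms, one sentence saying so in the Treatment Phase section settles the question of what is asked.

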Our primary goal is to assess the effect of NMES on: single fiber tension (force/CSA), velocity and CSA and mitochondrial content and ADP-stimulated oxygen consumption rate. A general linear mixed model will be used, with treatment group as between-subject and time as within-subject effects. A random effect will be included to account for clustering of observations within subjects (ie, fibers within each subject), as described (1), with the model conceptualized as a multi-level analysis with single fiber/organellar-level outcomes comprising level 1 variables and person-level covariates comprising level 2 variables (2). Covariates (eg, stage, chemotherapeutics, and activity level) can be included in the model as level 2 variables to control for potential confounders that differ by group. Whole muscle size and function and 6 min walk performance will be used in secondary analysis to evaluate whether changes in myofilament or mitochondrial content or function scale to variation in tissue-level or whole body function or size, as we have previously observed that molecular- and organellar-level function scale to the tissue and whole-body level in cancer (3), aging (4) and chronic disease (5).

For Aim 1, based on whole muscle results in cancer patients (3, 6), other diseased populations (7, 8) and our preliminary data, we anticipate that volunteers randomized to NMES will have greater single muscle fiber tension (20%) and CSA (20%) versus controls. We focused on these variables because they represent the two most disabling effects of cancer on muscle contractility: weakness and atrophy (3, 9). We would need $n=12$ /group to detect these differences between groups (power=90% and significance of 5%). Of note, we will likely have greater improvements in contractile velocity, per our preliminary data, which should further increase aggregate muscle power output and functionality and is readily detectable with this sample size. For Aim 2, based on our preliminary data showing the ability of NMES to improve mitochondrial content and function in the context of a profoundly atrophyic stimuli (ie, knee replacement surgery), we expect that patients randomized to NMES will have greater mitochondrial content (50%) and function (40%). Our sample size is driven by detecting changes in mitochondrial content, which would require $n=12$ /group with a power of 90% and a significance of 5%. Using this sample size, our minimal detectable differences for changes in mitochondrial function would be 14%. We have not performed sample size estimates on secondary outcomes because of the exploratory nature of these studies, but also because it is likely that we will either not be able to detect effects at this anatomic level because of confounding factors or we will detect effects at this level that are unrelated to the effects of NMES to improve skeletal muscle size and/or function (eg, enhanced neural activation related to NMES training improves whole muscle strength). This was a primary impetus

for our studies to evaluate the effects of NMES at the cellular/organellar level. However, we will evaluate these outcomes nonetheless, as they will provide important preliminary data for future trials if our hypotheses are supported by our results.

1. [name], M. J., Miller, M. S., VanBuren, P., Bedrin, N. G., LeWinter, M. M., Ades, P. A., and Palmer, B. M. (2012) Resistance training alters skeletal muscle structure and function in human heart failure: effects at the tissue, cellular and molecular levels. *J Physiol* **590**, 1243-1259
2. Hox, J. J. (2002) *Multilevel Analysis: Techniques and Applications.*, Lawrence Erlbaum Associates, Inc., Mahwah, NJ
